For those transfused, the hemoglobin analyzed will be the value immediately prior to the transfusion of the case. In the cases with multiple transfusions, it will be the highest of the identified pre-transfusion hemoglobin measures across each of the transfusions. We will define immediately prior to transfusion as the lab value drawn closest to transfusion within a 30-minute pre-transfusion window. If this proves too restrictive and more than 30% of pre-transfusion lab values will be excluded, the window will be liberalized to 45 minutes. The hemoglobin measurement identified is referred to as the “pre-transfusion hemoglobin” throughout this document. For those who were not transfused, the nadir hemoglobin will be the lowest value of the case.

The covariates to be included in all models (discussed below) are surgical specialty (defined based on anesthesia CPT Code assigned to the case), age, BMI, sex, presence of coronary artery disease (defined by ICD 9/10 codes), Elixhauser comorbidities, quarter of the study period, and nadir hemoglobin. The unit of measure for time used in trend analysis will be by quarter. The use of autologous blood will not be considered in this analysis. Patients who receive exclusively cell saver blood (and no PRBCs) will be considered not to be transfused for the purposes of the analysis.

We will describe the proportion of cases with a non-red blood cell blood product administered and the frequency of use of measures of coagulation (PT/INR, PTT, PLTs etc) as documented in the anesthesia record and the use of “cell saver” blood. Additionally, we will perform a survey of participating institutions to determine if formal blood transfusion protocols or blood transfusion management efforts, pre-operative preparation strategies were routinely used and which point of care coagulation tests were in place at the time the studied cases occurred.

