### **Primary Outcome 1: The change in documented hemoglobin prior to an intraoperative transfusion.**

The hemoglobin of interest for this outcome is the pre-transfusion hemoglobin. See additional definitions above. Additionally, for this primary outcome we will perform a sensitivity analysis, following the same statistical methodology, to compare the effect of including only the first transfusion of the case in those cases with multiple transfusion with our definition.

First, the trend of median pre-transfusion hemoglobin measurement by quarter will be assessed for any change over time by testing whether the slope is significantly different from 0 using a bivariate linear regression model with the dependent variable of median pre-transfusion hemoglobin measurement. If the slope is not significantly different from 0, then the analyses for this aim will conclude. Otherwise, a Joinpoint analysis will be conducted to determine if there are any inflection points in the trend. If no inflection points are found and the slope is negative and significantly different from 0, then Hypothesis 1 will be assumed true. If the Joinpoint analysis finds one or more inflection points in the data, then a Student's t test or Mann-Whitney U test will be used to compare the values between consecutive quarters to analyze the significance of the change. A similar analysis will be conducted at the institution level.

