**Secondary Outcome 1: Proportion of cases receiving a packed red blood cell transfusion throughout the study period.**

An analysis similar to that for Primary Outcome 1 will be used to determine if there was a difference in trend over time for the proportion of cases receiving a pRBC transfusion. A similar analysis will be conducted at the institution level.

The proportion of people transfused at each hemoglobin threshold level (<6, 6-7, 7-8, 8-9, 9-10, >10) will be compared between 2012 and 2016 to determine if a change in practice occurred using a Chi-square or Fisher's Exact test, as appropriate.

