**Secondary Outcome 2: The number of units of packed red blood cells transfused during the intraoperative period.**

The number of units of pRBC transfused during the intraoperative period will be analyzed similar to Primary Outcome 1.

To determine independent predictors of the number of units of pRBC transfused during a case, two mixed effects linear regression models will be constructed with the independent covariates listed in the methods and the dependent variable of number of units of packed red blood cells transfused. The first model will contain the mixed effect of institution, and the second model will contain the hierarchical mixed effects of primary attending nested within institution.

**Secondary Outcome 3: The nadir postoperative hemoglobin (lowest value measured 0 – 72 hrs after the completion of intraoperative anesthesia care)**

The lowest postop hemoglobin will be examined for a trend over time for all cases using a Joinpoint analysis as for previous outcomes. The lowest postop hemoglobin will be compared at each time point between those with and without an intraoperative transfusion using a Student's t test or Mann-Whitney U test, as appropriate.

**Secondary Outcome 4: The relationship between patient, surgical and institutional factors and the occurrence of transfusion and determination of the subsequent impact of any transfusion trends on blood product utilization.**

Two mixed-effects logistic regression models will be used to determine if surgery type, year, and cardiac disease are independent predictors of intraoperative transfusion. The outcome of intraoperative transfusion will be defined as any PRBC use between Anesthesia Start and

Anesthesia End. The first model will contain the mixed effect of institution, and the second model will contain the hierarchical mixed effects of primary attending nested within institution. Independent variables to be included in the model are: Age, Sex, Elixhauser co-morbidities (as numeric and also CAD y/n, heart failure y/n, cancer y/n), WHO BMI classifications, ASA Status, Pre-op Hb, lowest Intra-op Hb for cases without intraop transfusion or the pre-transfusion hemoglobin, Pre-op Plts (abnormal y/n), Pre-op Creatinine (abnormal y/n), Abnormal coags (y/n – PT, PTT or INR), Surgical Specialty, EBL, Cell saver (Scavenged) blood use (y/n), Emergent Surgery, Use of anti-fibrinolytics (Aminocaproic Acid, Tranexamic Acid, Aprotinin) – y/n, and surgical Case Duration.

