## Sample Size:

Based on a rough approximation of the inclusion criteria using DataDirect, we found around 113,000 cases with intraoperative Hemoglobin/Hematocrit values, which should provide sufficient power for all planned analyses.

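### The 30/45-minute window can remove transfused cases, but not non-transfused ones, from the by-band proportions of Secondary Outcome 1: levels are understated, and the 2012 versus 2016 comparison is biased if lab capture differs between the years

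*Protocol*

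**What the plan says.** The Methods section of the protocol defines the hemoglobin to be analyzed differently in the two groups.

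- Transfused cases: "the lab value drawn closest to transfusion within a 30-minute pre-transfusion window". With several transfusions, "it will be the highest of the identified pre-transfusion hemoglobin measures across each of the transfusions". If "more than 30% of pre-transfusion lab values will be excluded, the window will be liberalized to 45 minutes". No further widening follows, and no limit is set on the loss that remains at 45 minutes.
- Non-transfused cases: "For those who were not transfused, the nadir hemoglobin will be the lowest value of the case". No window applies.

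Secondary Outcome 1 has two parts. The first is the trend in the overall proportion of cases transfused. The second is by band: "The proportion of people transfused at each hemoglobin threshold level" (below 6, four one-unit bands from 6 to 10, above 10) is compared between 2012 and 2016 by a chi-square or Fisher's exact test. That section does not restate which hemoglobin defines the band. The outcome list in the Methods speaks of stratifying by earlier laboratory measurements, and the definitions above are the only ones given.

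The transfusion model in Secondary Outcome 4 uses the same two-source covariate: "lowest Intra-op Hb for cases without intraop transfusion or the pre-transfusion hemoglobin".

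The one sensitivity analysis on this definition, under Primary Outcome 1, is "to compare the effect of including only the first transfusion of the case in those cases with multiple transfusion with our definition". It does not address transfused cases without an in-window lab.

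**The concern.** The window suits Primary Outcome 1, a median among transfused cases. There, a missing value raises a question of selection but does not distort a denominator. A proportion transfused within a band is different, because both groups make up its denominator. A transfused case with no in-window lab leaves the numerator and the denominator, while a non-transfused case with any intraoperative value always stays.

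At stake is the part of Hypothesis 2 that expects fewer transfusions at each hemoglobin value. The reported proportions would be too low in every band with such losses. A test of 2012 against 2016 also cannot tell a change in transfusion practice from a change in how often a lab was drawn shortly before transfusion. The sample size statement ("around 113,000 cases with intraoperative Hemoglobin/Hematocrit values, which should provide sufficient power for all planned analyses") does not help, since more cases reduce random error but not this bias.

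**Working it through.** **Inputs.** From the protocol: the 30-minute window, the move to 45 minutes, the 30% trigger, the nadir rule, the six bands, and the years 2012 and 2016. The protocol gives no proportion transfused by band and no share of transfused cases without an in-window value, so p and m below are assumptions shown over a range. There is no plan figure to reproduce: the 30% is a rule and the 113,000 is a database count.

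**Levels.** Let p be the proportion transfused in a band under the same definition with no loss, and m the share of that band's transfused cases without an in-window value. Then

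observed p* = p(1-m) / [p(1-m) + (1-p)], so observed odds = (1-m) × p/(1-p).

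For p = 50%:
- m = 30%: 0.35/(0.35 + 0.50) = 41.2%
- m = 15%: 0.425/(0.425 + 0.50) = 45.9%

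| True p | m = 10% | m = 15% | m = 30% |
|---|---|---|---|
| 20% | 18.4% | 17.5% | 14.9% |
| 50% | 47.4% | 45.9% | 41.2% |
| 80% | 78.3% | 77.3% | 73.7% |

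**2012 versus 2016.** With unchanged practice, the apparent odds ratio is (1-m2016)/(1-m2012).
- Equal m: 1.00
- 30% to 25%: 0.75/0.70 = 1.07
- 30% to 15%: 0.85/0.70 = 1.21; a 50% band appears to rise by 45.95 - 41.18 = 4.8 points
- 10% to 30%: 0.70/0.90 = 0.78, a false decline in the direction that Hypothesis 2 predicts

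A real change can also be masked. If the true proportion falls from 50% to 45% while m falls from 30% to 15%, the second year shows 0.3825/(0.3825 + 0.55) = 41.0%, against 41.2% in the first.

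The chance of a spurious p < 0.05 depends strongly on the size of the shift. For a 50% band with an assumed 1,000 cases per year before loss (normal approximation), it is about 10.5% for 30% to 25% and about 75% for 30% to 10%.

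**From lab values to cases.** A case with several transfusions is lost only if none of them has an in-window lab. Assume that 45% of transfused cases have two transfusions and that 30% of transfusions, independently, lack a value. The share of cases lost is then 0.55 × 0.30 + 0.45 × 0.30² = 0.165 + 0.0405 = 20.5%. A simulation on these assumptions, with assumed hemoglobin distributions and the highest-value rule applied, gave a lower proportion transfused in all six bands than without loss. For example, 7-8 fell from 59.4% to 53.2% and 8-9 from 26.7% to 21.7%.

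**The case against.** Several points on the other side stand.

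- A reader might infer that the by-band comparison does drift with lab timing. The protocol does not show this. It gives no capture rates by year, and with constant m the 2012 versus 2016 odds ratio is free of this bias. Nor does it support more bedside hemoglobin testing as a cause: the planned site survey asks about point-of-care coagulation tests.
- A reader might take 30% as the expected loss of transfused cases. It is a trigger for widening the window, and it is stated on lab values. The loss per case may be smaller, as the 20.5% example shows. No ceiling applies after widening, however, so a larger loss is not ruled out either.
- The understatement is relative to the same definition without loss. Taking the highest value for transfused cases against the nadir for the others can push the other way: in the simulation without loss, the 9-10 band shows 8.7% with the highest value and 6.8% with the first-transfusion value.
- The banding hemoglobin in Secondary Outcome 1 is inferred from the Methods. It is the likely reading, not an explicit one.
- Non-transfused cases are complete only among those with some intraoperative value.
- The by-band test is one unadjusted secondary comparison in a study labelled descriptive. Capture tables could sit in an SAP that is not shown.

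The last point does not remove the issue. The unequal rule is fixed in the protocol itself, and nothing else in the protocol repairs it.

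**Conclusion.** The point holds in a limited form. If the bands use the hemoglobin defined in the Methods, losses from the window fall on transfused cases only, and the odds of transfusion in a band are multiplied by (1-m). The direction is arithmetic; the size is unknown because m is not given. At m between 15% and 30%, a true 50% would be reported about 4 to 9 points too low.

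Bias in the 2012 versus 2016 odds ratio is conditional on m differing between those years. It ranges from slight (1.07 for 30% to 25%) to enough to hide a modest real decline (1.21 for 30% to 15%).

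The overall proportion transfused needs no hemoglobin value and is unaffected, so the documents do not support a reading that Hypothesis 2 as a whole is undermined. Primary Outcome 1 does not have this denominator problem. The transfusion model in Secondary Outcome 4 does share it: with the same covariate and no stated handling of missing values, a complete-case fit would lose the same transfused cases. The plan should be changed before analysis.

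**What to change.** - Keep the 30/45-minute window for Primary Outcome 1.
- State in Secondary Outcome 1 which hemoglobin defines the bands. For transfused cases, use the last intraoperative value before the first transfusion, whatever the interval; for non-transfused cases, use the intraoperative nadir.
- Put cases with no usable intraoperative value, in both groups, in a separate no-value category and report it. This includes transfused cases whose only intraoperative values follow the first transfusion; they are a residual loss that the table should show.
- Do not substitute the pre-operative hemoglobin in transfused cases only. That would bring in transfused cases without an intraoperative lab while similar non-transfused cases stay out, and it would set pre-bleeding values against nadirs.
- Report the share of transfused cases without an in-window value by year and site, and say whether the 30% trigger counts values, transfusions or cases.
- Repeat the by-band comparison with the in-window definition as a sensitivity analysis. State how the Secondary Outcome 4 model handles the same missing values.

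The cost is a few sentences, one derived variable and one table, with no new data. The downside is that some values will be older than 45 minutes and may place a case in a higher band than its level at transfusion. The sensitivity analysis shows how much this matters.

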### **Statistical Analysis:**

Summary statistics will be presented as means and standard deviations or medians with interquartile ranges for continuous variables, as appropriate, and frequencies with percentages for categorical variables. All continuous variables will be assessed for normality using the Kolmogorov-Smirnov test. Univariate demographic and covariate comparisons between those who did and did not receive a transfusion will be analyzed using Student’s t-tests or Mann-

Whitney U tests for continuous variables, and Chi-squared or Fisher's Exact tests for categorical variables, as appropriate.

Mixed-effects multivariable linear or logistic regression models will be constructed as necessary. Prior to model entry, all covariates selected for model inclusion will be checked for collinearity using a Pearson correlation matrix. Variable pairs with a correlation  $> 0.70$  will be considered collinear and either combined into one variable, or one of the covariates will be excluded from the model. All variable pairs with a correlation  $\leq 0.70$  will be deemed fit for model entry. Model effect size will be presented as adjusted odds ratios with 95% confidence intervals, or beta coefficients with standard error, as appropriate. The covariates to be included in all models (discussed below) are surgical specialty, age, BMI, sex, presence of coronary artery disease, Elixhauser comorbidities, quarter of the study period, and hemoglobin. Time will be included in all models as a fixed effect by quarter, half-year, or year based on available sample size. The first quarter, half-year, or year will serve as the reference group. The random effects of institution and attending, where appropriate, will be presented as intraclass correlation coefficients and median odds ratios with 95% confidence intervals. Measures of effect size will be reported as adjusted odds ratios for logistic regression and beta coefficients for linear regression, and will be presented with 95% confidence intervals. For logistic regression models, model predictive capability will be presented as the area under the receiver operating curve (ROC) c-statistic. For linear regression, the extent to which the model explains the variability of the data will be presented as  $R^2$  values. Covariates with a statistically significant adjusted odds ratio or beta coefficient (as appropriate) will be considered independent predictors of the outcome.

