## Methods:

The MPOG Consortium assembles a database of perioperative information of patients undergoing anesthetic care at institutions across the US and the Netherlands. Data is assembled from electronic health record systems (including anesthesia specific systems), administrative, laboratory and outcome data sources. Full details of the functioning of the MPOG Consortium are described elsewhere. IRB approval for this study is provided by University of Michigan Institutional Review Board (HUM00052066). Sites participating in the MPOG collaborative obtain local IRB approval to assemble, organize and transmit this dataset. In keeping with the normal operating procedure of the MPOG collaborative the study protocol was presented to and approved by the MPOG Perioperative Clinical Research Committee (PCRC) on October 9th 2017. It was finalized on Feb 2nd 2018, prior to data extraction or analysis. A completed STROBE checklist for this study is attached to this manuscript (Appendix 1).

Sites will be included if they participated in the MPOG collaborative and data, including perioperative labs, and hospital and professional billing data were consistently available for the period between January 1, 2012 and July 1, 2017. We anticipate including data from 8 participating US sites: Cleveland Clinic, University of Colorado, University of Michigan, University of Oklahoma, University of Tennessee, University of Vermont, University of Virginia and Vanderbilt University.

Subjects will be included in the study if they were 18 years or older at time of surgery, underwent an orthopedic, general, transplant, vascular, gynecologic, urologic, neurosurgery, plastic, ENT or thoracic procedure with an associated inpatient stay. Subjects will be excluded if they underwent transfusion of greater than 3 units of packed red blood cells during the intraoperative period, underwent outpatient surgery, cardiac surgery, obstetric surgery, any procedure involving CPB or were assessed as having an ASA physical status classification of 5 or 6. Case groupings will be performed based on Anesthesia CPT Codes (see Appendix 2).

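### The models' rule for naming an independent predictor gives no single test for time or surgical specialty; if any significant contrast counts, time with no effect is named a predictor about 18% to 43% of the time, depending on the unit

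*Protocol*

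**What the plan says.** The Statistical Analysis section fixes three things for the mixed-effects models.

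- Form of time: "Time will be included in all models as a fixed effect by quarter, half-year, or year based on available sample size".
- Reference level: "The first quarter, half-year, or year will serve as the reference group".
- Decision rule: "Covariates with a statistically significant adjusted odds ratio or beta coefficient (as appropriate) will be considered independent predictors of the outcome".

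No joint test, trend term or multiplicity rule is given for covariates with more than two levels. The unit of time is not settled either. Methods says "The unit of measure for time used in trend analysis will be by quarter", both covariate lists name quarter, and Secondary Outcome 4 speaks of year: "Two mixed-effects logistic regression models will be used to determine if surgery type, year, and cardiac disease are independent predictors of intraoperative transfusion". Aim 2 singles out institution, temporal trend, surgery type and cardiac disease.

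Outside these models, Primary Outcome 1 tests a linear slope on quarterly medians, followed by Joinpoint if the slope differs from zero. Primary Outcome 2 repeats this, and Secondary Outcome 1 uses a similar analysis for the proportion of cases transfused.

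**The concern.** The question put to the Secondary Outcome 4 models is whether time, surgery type and cardiac disease each predict transfusion. Cardiac disease is binary, so it has one odds ratio and the rule works as a single test. Time has 5, 10 or 21 odds ratios and specialty has 9. Each of these tests a narrower null, that one level equals the reference level, and none tests the absence of any time or specialty effect.

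If one significant contrast is enough, the chance of naming a covariate a predictor by luck rises with its number of levels. The covariates in Aim 2 are then held to different standards, and for time the standard depends on a unit that is still open. The contrasts also share one reference, so an atypical first period can make many of them significant together. The rule ignores direction as well: one isolated period with a raised odds ratio would qualify, although Hypothesis 2 is a decline.

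**Working it through.** The protocol states no error rate or power for this rule, so there is no figure of its own to reproduce.

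**Inputs**
- Study period: Methods requires data "consistently available for the period between January 1, 2012 and July 1, 2017". That is 5.5 years: 22 quarters, 11 half-years, or 6 calendar years with the last a half-year. Against the first period this gives 21, 10 or 5 contrasts.
- Specialties: ten in Methods and Appendix 2, hence 9 contrasts.
- Level: not stated. Two-sided 0.05 (critical value 1.96) is assumed, because effect sizes "will be presented with 95% confidence intervals".
- Sizes of periods and specialties: not stated. Equal sizes are assumed first, then varied.
- Reading of the rule: any significant contrast makes the covariate a predictor. This too is an assumption.

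**False-positive rate**

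With no effect, contrast k is Z_k = (e_k − e_0)/√(1/n_k + 1/n_0), where e_0 is the error of the shared reference. With equal sizes any two contrasts have correlation 0.5. Let the reference be q times the size of the other levels. Conditioning on its error x gives

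P(any |Z_k| > 1.96) = 1 − ∫ [Φ(1.96√(1+1/q) + x/√q) − Φ(−1.96√(1+1/q) + x/√q)]^K φ(x) dx.

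| Covariate | K | q = 0.5 | q = 1 | q = 2 |
|---|---|---|---|---|
| Year | 5 | 15.5% | 18.3% | 20.5% |
| Half-year | 10 | 22.6% | 28.7% | 34.2% |
| Quarter | 21 | 31.8% | 42.9% | 53.5% |
| Specialty | 9 | 21.4% | 26.9% | 31.8% |

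With the last year at half size and the other years equal, the yearly figure is 18.8%. Simulation gave 43.0% for 21 equal quarters. A smaller reference gives the lower figure, because its noise then dominates all the contrasts and makes them more alike (correlation 0.67 at q = 0.5, 0.33 at q = 2). If the 21 contrasts were independent, the rate would be 1 − 0.95^21 = 65.9%.

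**Efficiency for a steady trend**

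Take 22 equal quarters and measure effects in standard errors of one quarter. The sum of squared deviations of 22 equally spaced quarters is 885.5, so a trend term has z = b√885.5 for slope b per quarter. Power of 80% needs b = (1.96 + 0.84)/√885.5 = 0.094. For that same trend:
- last quarter versus first: z = 21 × 0.094/√2 = 1.40, power 29%;
- joint test on 21 degrees of freedom: 30%;
- contrasts adjusted by Dunnett's method (critical value 2.92): 22%;
- any unadjusted contrast: 72%, a figure raised by the 43% false-positive rate.

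**Absolute size**

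The Sample Size section gives about 113,000 cases, or 113,000/22 ≈ 5,136 per quarter if spread evenly. Assume 10% are transfused, with no adjustment or clustering. A total odds ratio of 0.8 over the period then gives 92% power for last versus first quarter (69% to 99.5% for assumed rates of 5% to 20%). At 0.9 it is 36% (21% to 57%), against 89% for a trend term at the 10% rate.

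**The case against.** **The any-contrast reading is inferred.** The rule does not say how a multi-level covariate is judged. It could be read level by level, so that a finding concerns one year against the first and there is no overall verdict to inflate. Omnibus tests of factors are also often left to a statistical analysis plan. This stands as a caution on the percentages. But Secondary Outcome 4 asks for an overall verdict on surgery type and year, and the protocol has itself fixed a coding and a decision rule that do not fit together. The rule is either inflated or undefined, and the remedy is the same.

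**Temporal trend is tested elsewhere.** The slope and Joinpoint analyses cover both primary outcomes and, in similar form, the proportion transfused. The synopsis adds ANOVA for that proportion, and Secondary Outcome 4 adds an observed-versus-expected comparison of the first and last periods. So no primary conclusion rests on the contrast coding. However, the slope tests and ANOVA are unadjusted, and the observed-versus-expected analysis looks only at the two end periods. None gives one adjusted test of time in the logistic models.

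**The study is descriptive, and odds ratios are reported with confidence intervals.** This limits the harm, but the label of independent predictor would still be applied by the rule.

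**Two stronger readings are tempting.** A reader might infer that 43% is the error rate of the plan. It is the quarterly case only; half-years and years are permitted, and Secondary Outcome 4 names year. A reader might also infer that a real trend would be tested with little power. The 29% belongs to a single contrast that the protocol never designates as its test. Under the any-contrast reading that produces the 43%, the trend is declared 72% of the time where a trend term has 80%. With about 113,000 cases, even the single contrast is strong for a moderate change.

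**Conclusion.** The point holds for the secondary regression models, chiefly Secondary Outcome 4 and through it Aim 2. Under the any-contrast reading, two-sided 0.05 and equal groups, a covariate with no effect is named an independent predictor about 18% to 19% of the time for years, 29% for half-years, 43% for quarters and 27% for ten specialties. Changing the reference group from half to twice the size of the others moves the quarterly figure between 32% and 54% and the specialty figure between 21% and 32%. Every permitted unit of time therefore exceeds 5% by a factor of three or more, and a large sample does not reduce this.

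On power, the supportable statement is only that individual period contrasts are inefficient for a steady trend compared with one trend term. The primary outcomes are unaffected.

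**What to change.** In the Statistical Analysis section:

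1. Set the unit of time for the models in advance, and use the same unit in Methods and Secondary Outcome 4.
2. Judge time in each model by one prespecified test: a one-degree-of-freedom trend term with period as a number, or a joint test over periods if non-linear change is of interest.
3. Judge surgical specialty by one joint likelihood-ratio or Wald test over its levels.
4. Present the period and specialty odds ratios with confidence intervals as descriptive results.
5. Keep the single-coefficient rule for binary and continuous covariates, and state the significance level.

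The trend term and the joint tests each hold the nominal level by construction. The cost is wording, one trend term and one joint test per model. The downside is small: a trend term can miss a purely non-linear pattern, which the period odds ratios and the Joinpoint analysis would still display. Choosing the joint test for time avoids that but costs power for a steady trend (30% against 80% in the quarterly example).
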